10.3.2. Definition of SAE

If an event is not an AE per definition above, then it cannot be an SAE even if serious conditions are met (eg, hospitalization for signs/symptoms of the disease under study, death due to progression of disease).

An SAE is defined as any untoward medical occurrence that, at any dose:

a. Results in death

b. Is life-threatening

The term “life-threatening” in the definition of “serious” refers to an event in which the participant was at risk of death at the time of the event. It does not refer to an event that hypothetically might have caused death if it were more severe.

c. Requires inpatient hospitalization or prolongation of existing hospitalization

In general, hospitalization signifies that the participant has been detained (usually involving at least an overnight stay) at the hospital or emergency ward for observation and/or treatment that would not have been appropriate in the physician's office or outpatient setting. Complications that occur during hospitalization are AEs. If a complication prolongs hospitalization or fulfills any other serious criteria, the event is serious. When in doubt as to whether “hospitalization” occurred or was necessary, the AE should be considered serious.

Hospitalization for elective treatment of a preexisting condition that did not worsen from baseline is not considered an AE.

d. Results in persistent disability/incapacity

- The term disability means a substantial disruption of a person's ability to conduct normal life functions.
- This definition is not intended to include experiences of relatively minor medical

significance such as uncomplicated headache, nausea, vomiting, diarrhea, influenza, and accidental trauma (eg, sprained ankle) which may interfere with or prevent everyday life functions but do not constitute a substantial disruption.

e. Is a congenital anomaly/birth defect

f. Other situations:

- Medical or scientific judgment should be exercised in deciding whether SAE reporting is appropriate in other situations such as important medical events that may not be immediately life-threatening or result in death or hospitalization but may jeopardize the participant or may require medical or surgical intervention to prevent one of the other outcomes listed in the above definition. These events should usually be considered serious.
- Examples of such events include invasive or malignant cancers, intensive treatment in an emergency room or at home for allergic bronchospasm, blood dyscrasias or convulsions that do not result in hospitalization, or development of drug dependency or drug abuse.

10.3.3. Recording/Reporting and Follow-up of AEs and/or SAEs

AE and SAE Recording/Reporting

The table below summarizes the requirements for recording adverse events on the CRF and for reporting serious adverse events on the Clinical Trial (CT) Serious Adverse Event (SAE) Report Form to Pfizer Safety. These requirements are delineated for 3 types of events: (1) SAEs; (2) nonserious adverse events (AEs); and (3) exposure to the investigational product under study during pregnancy or breastfeeding, and occupational exposure.

It should be noted that the CT SAE Report Form for reporting of SAE information is not the same as the AE page of the CRF. When the same data are collected, the forms must be completed in a consistent manner. AEs should be recorded using concise medical terminology and the same AE term should be used on both the CRF and the CT SAE Report Form for reporting of SAE information.

Safety Event	Recorded on the CRF	Reported on the CT SAE Report Form to Pfizer Safety Within 24 Hours of Awareness
SAE	All	All
Nonserious AE	All	None

Exposure to the investigational product under study during pregnancy or breastfeeding, and occupational exposure	None	All (and exposure during pregnancy [EDP] supplemental form for EDP)	

When an AE/SAE occurs, it is the responsibility of the investigator to review all documentation (eg, hospital progress notes, laboratory reports, and diagnostic reports) related to the event.The investigator will then record all relevant AE/SAE information in the CRF.It is not acceptable for the investigator to send photocopies of the participant's medical records to Pfizer Safety in lieu of completion of the CT SAE Report Form/AE/SAE CRF page.There may be instances when copies of medical records for certain cases are requested by Pfizer Safety. In this case, all participant identifiers, with the exception of the participant number, will be redacted on the copies of the medical records before submission to Pfizer Safety.The investigator will attempt to establish a diagnosis of the event based on signs, symptoms, and/or other clinical information. Whenever possible, the diagnosis (not the individual signs/symptoms) will be documented as the AE/SAE.			
<h4>Assessment of Intensity</h4> 
The investigator will make an assessment of intensity for each AE and SAE reported during the study and assign it to 1 of the following categories:
 
Mild: An event that is easily tolerated by the participant, causing minimal discomfort and not interfering with everyday activities.Moderate: An event that causes sufficient discomfort and interferes with normal everyday activities.Severe: An event that prevents normal everyday activities. An AE that is assessed as severe should not be confused with an SAE. Severe is a category utilized for rating the intensity of an event; and both AEs and SAEs can be assessed as severe. 
An event is defined as "serious" when it meets at least 1 of the predefined outcomes as described in the definition of an SAE, NOT when it is rated as severe.
			

Assessment of Causality

- The investigator is obligated to assess the relationship between study intervention and each occurrence of each AE/SAE.
- A “reasonable possibility” of a relationship conveys that there are facts, evidence, and/or arguments to suggest a causal relationship, rather than a relationship cannot be ruled out.
- The investigator will use clinical judgment to determine the relationship.
- Alternative causes, such as underlying disease(s), concomitant therapy, and other risk factors, as well as the temporal relationship of the event to study intervention administration will be considered and investigated.
- The investigator will also consult the investigator’s brochure (IB) and/or product information, for marketed products, in his/her assessment.
- For each AE/SAE, the investigator **must** document in the medical notes that he/she has reviewed the AE/SAE and has provided an assessment of causality.
- There may be situations in which an SAE has occurred and the investigator has minimal information to include in the initial report to the sponsor. However, **it is very important that the investigator always make an assessment of causality for every event before the initial transmission of the SAE data to the sponsor.**
- The investigator may change his/her opinion of causality in light of follow-up information and send an SAE follow-up report with the updated causality assessment.
- The causality assessment is one of the criteria used when determining regulatory reporting requirements.
- If the investigator does not know whether or not the investigational product caused the event, then the event will be handled as “related to investigational product” for reporting purposes, as defined by the sponsor. In addition, if the investigator determines that an SAE is associated with study procedures, the investigator must record this causal relationship in the source documents and CRF, and report such an assessment in the dedicated section of the CT SAE Report Form and in accordance with the SAE reporting requirements.

Follow-up of AEs and SAEs

- The investigator is obligated to perform or arrange for the conduct of supplemental measurements and/or evaluations as medically indicated or as requested by the

sponsor to elucidate the nature and/or causality of the AE or SAE as fully as possible. This may include additional laboratory tests or investigations, histopathological examinations, or consultation with other healthcare professionals.

- If a participant dies during participation in the study or during a recognized follow-up period, the investigator will provide Pfizer Safety with a copy of any postmortem findings including histopathology.
- New or updated information will be recorded in the originally completed CRF.
- The investigator will submit any updated SAE data to the sponsor within 24 hours of receipt of the information.

10.3.4. Reporting of SAEs

SAE Reporting to Pfizer Safety via an Electronic Data Collection Tool

- The primary mechanism for reporting an SAE to Pfizer Safety will be the electronic data collection tool.
- If the electronic system is unavailable, then the site will use the paper SAE data collection tool (see next section) in order to report the event within 24 hours.
- The site will enter the SAE data into the electronic system as soon as the data become available.
- After the study is completed at a given site, the electronic data collection tool will be taken off-line to prevent the entry of new data or changes to existing data.
- If a site receives a report of a new SAE from a study participant or receives updated data on a previously reported SAE after the electronic data collection tool has been taken off-line, then the site can report this information on a paper SAE form (see next section) or to Pfizer Safety by telephone.

SAE Reporting to Pfizer Safety via CT SAE Report Form

- Facsimile transmission of the CT SAE Report Form is the preferred method to transmit this information to Pfizer Safety.
- In circumstances when the facsimile is not working, notification by telephone is acceptable with a copy of the CT SAE Report Form sent by overnight mail or courier service.
- Initial notification via telephone does not replace the need for the investigator to complete and sign the CT SAE Report Form pages within the designated reporting time frames.

10.4. Appendix 4: Contraceptive Guidance and Collection of Pregnancy Information

10.4.1. Male Participant Reproductive Inclusion Criteria

Male participants are eligible to participate if they agree to the following requirements during the intervention period and for at least 28 days after the last dose of study intervention :

- Refrain from donating sperm.

PLUS either:

- Be abstinent from heterosexual intercourse with a female of childbearing potential as their preferred and usual lifestyle (abstinent on a long-term and persistent basis) and agree to remain abstinent.

OR

- Must agree to use a male condom when engaging in any activity that allows for passage of ejaculate to another person.

In addition to male condom use, a highly effective method of contraception will be considered in woman of childbearing potential (WOCBP) partners of male participants (refer to the list of highly effective methods below in [Section 10.4.4](#)).

10.4.2. Female Participant Reproductive Inclusion Criteria

A female participant is eligible to participate if she is not pregnant or breastfeeding, or a WOCBP (see definitions below in [Section 10.4.3](#)).

The investigator is responsible for review of medical history, menstrual history, and recent sexual activity to decrease the risk for inclusion of a woman with an early undetected pregnancy.

10.4.3. Woman of Childbearing Potential (WOCBP)

A woman is considered fertile following menarche and until becoming postmenopausal unless permanently sterile (see below).

If fertility is unclear (eg, amenorrhea in adolescents or athletes) and a menstrual cycle cannot be confirmed before the first dose of study intervention, additional evaluation should be considered.

Women in the following categories are not considered WOCBP:

1. Premenopausal female with 1 of the following:
 - Documented hysterectomy;

- Documented bilateral salpingectomy;
- Documented bilateral oophorectomy.

For individuals with permanent infertility due to an alternate medical cause other than the above, (eg, mullerian agenesis, androgen insensitivity), investigator discretion should be applied to determining study entry.

Note: Documentation for any of the above categories can come from the site personnel's review of the participant's medical records, medical examination, or medical history interview. The method of documentation should be recorded in the participant's medical record for the study.

2. Postmenopausal female.

- A postmenopausal state is defined as age 60 years or older or no menses for 12 months without an alternative medical cause.
 - A high follicle-stimulating hormone (FSH) level in the postmenopausal range may be used to confirm a postmenopausal state in women not using hormonal contraception or hormone replacement therapy (HRT).
 - Female on HRT and whose menopausal status is in doubt will be required to use one of the nonestrogen hormonal highly effective contraception methods if they wish to continue their HRT during the study. Otherwise, they must discontinue HRT to allow confirmation of postmenopausal status before study enrollment.

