4.2.1. Population(s)

The population planned for this study will be male and female adult participants. Female participants will be women of non-childbearing potential (WONCBP), since at the present time embryofetal development toxicity studies with PF-07081532 have not been conducted. In male participants appropriate measures are expected to be followed to limit potential transfer of PF-07081532 in semen to partners (see [Appendix 4](#)).

Participants enrolled in this study will be adults with inadequately controlled T2DM (as indicated by HbA1c at screening) on metformin monotherapy, which is considered first-line therapy for glycemic control according to current treatment guidelines.¹¹ At screening, this study requires that participants have been taking a minimum stable metformin dose of at least 500 mg/day for at least 2 months prior to the screening visit. The dose of metformin, where possible, is expected to remain the same until completion of study participation (ie, follow-up visit). Available *in vitro* data suggest that PF-07081532 is not expected to impact the PK of metformin via inhibition of organic cation transporter (OCT)2, and the risk of a clinical interaction is deemed negligible.

There is precedent for a GLP-1R agonist being indicated for obesity (Saxenda®, liraglutide 3 mg). PF-07081532 may also be assessed in non-diabetic obese participants in this study. This would afford the opportunity to assess the safety, tolerability, pharmacokinetics, **CCI** [REDACTED] in an obese population. The PK **CCI** [REDACTED] data collected in these cohorts may be used to select doses and titration algorithms for future studies of PF-07081532 in obesity.

CCI [REDACTED]

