5.1. Inclusion Criteria

Participants are eligible to be included in the study only if all of the following criteria apply:

Age and Sex:

1. Male and female participants must be between the ages of 18 and 70 years, inclusive, at the time of signing the informed consent document (ICD). Females must be of non-childbearing potential.
 - Refer to [Appendix 4](#) for reproductive criteria for males ([Section 10.4.1](#)) and females ([Section 10.4.2](#)).

Type of Participant and Disease Characteristics:

2. **Parts A and C only:** Participants enrolling with **T2DM** must be taking metformin monotherapy as their only anti-hyperglycemic treatment. Metformin dose must be at least 500 mg per day and must be stable, defined as no change in the treatment, including dose, for at least 2 months prior to the screening visit. For further information, see [Section 6.5](#).
3. **Parts A and C only:** For participants enrolling with **T2DM**: HbA1c $\geq 7.0\%$ and $\leq 10.5\%$ at screening (confirmed by a single repeat, if necessary).
Part B only: For participants enrolling as non-diabetic **obese**: HbA1c $< 6.5\%$ at screening.

4. Participants who are willing and able to comply with all scheduled visits, treatment plan, laboratory tests, lifestyle considerations, and other study procedures.

Weight:

5. A total body weight >50 kg (110 lbs).
6. **Parts A and C only:** For participants enrolling with **T2DM**: body mass index (BMI) of ≥ 24.5 to ≤ 45.5 kg/m^2 .
7. **Part B only:** For participants enrolling as non-diabetic **obese**: BMI >30.5 to ≤ 45.5 kg/m^2 .

Informed Consent:

8. Capable of giving signed informed consent as described in [Appendix 1](#), which includes compliance with the requirements and restrictions listed in the ICD and in this protocol.

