5.3.4. Contraception

The investigator or his or her designee, in consultation with the male participant, will confirm that the participant has selected an appropriate method of contraception for the individual male participant and his partner(s) from the permitted list of contraception methods (see [Appendix 4, Section 10.4.4](#)) and will confirm that the participant has been instructed in its consistent and correct use. At time points indicated in the [Schedule of Activities](#), the investigator or designee will inform the male participant of the need to use effective contraception consistently and correctly and document the conversation and the male participant's affirmation in the participant's chart (participants need to affirm their consistent and correct use of at least 1 of the selected methods of contraception). In addition, the investigator or designee will instruct the participant to call immediately if the selected

contraception method is discontinued or if pregnancy is known or suspected in the participant's female partner.

Female participants will not require use of contraception as they cannot be women of childbearing potential.

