10.4.4. Contraception Methods

The following contraception methods are be used by women of childbearing potential who are partners of male participants in this study:

Highly Effective Methods That Have Low User Dependency

1. Implantable progestogen-only hormone contraception associated with inhibition of ovulation.
2. Intrauterine device (IUD).
3. Intrauterine hormone-releasing system (IUS).
4. Bilateral tubal occlusion.
5. Vasectomized partner.

- Vasectomized partner is a highly effective contraceptive method provided that the partner is the sole sexual partner of the WOCBP and the absence of sperm has been confirmed. If not, an additional highly effective method of contraception should be used. The spermatogenesis cycle is approximately 90 days.

Highly Effective Methods That Are User Dependent

1. Combined (estrogen- and progestogen-containing) hormonal contraception associated with inhibition of ovulation.
 - Oral;
 - Intravaginal;
 - Transdermal;
 - Injectable.
2. Progestogen-only hormone contraception associated with inhibition of ovulation.
 - Oral;
 - Injectable.
3. Sexual abstinence.
 - Sexual abstinence is considered a highly effective method only if defined as refraining from heterosexual intercourse during the entire period of risk associated with the study intervention. The reliability of sexual abstinence needs to be evaluated in relation to the duration of the study and the preferred and usual lifestyle of the participant.

One of the following effective barrier methods must be used in addition to the highly effective methods listed above that are user dependent:

- Male or female condom with or without spermicide;
- Cervical cap, diaphragm, or sponge with spermicide;
- A combination of male condom with either cervical cap, diaphragm, or sponge with spermicide (double-barrier methods).

Collection of Pregnancy Information

For both unapproved/unlicensed products and for marketed products, an exposure during pregnancy (EDP) occurs if:

- A female becomes, or is found to be, pregnant either while receiving or having been exposed (eg, because of treatment or environmental exposure) to the investigational product; or the female becomes or is found to be pregnant after discontinuing and/or being exposed to the investigational product;

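### The HRT bullet in Section 10.4.3 lets a woman of doubtful menopausal status take part on contraception, although the protocol admits only women of non-childbearing potential

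*Protocol*

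**What the plan says.** Inclusion criterion 1 (Protocol Section 5.1) is unconditional: "Females must be of non-childbearing potential". It refers sites to Appendix 4 for the detailed reproductive criteria. Section 4.2.1 gives the reason for the restriction: "since at the present time embryofetal development toxicity studies with PF-07081532 have not been conducted".

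In Appendix 4, Section 10.4.2 repeats the rule, "A female participant is eligible to participate if she is not pregnant or breastfeeding, or a WOCBP", and defers to Section 10.4.3 for the definition of a woman of childbearing potential (WOCBP). Section 10.4.3 presumes fertility from menarche until menopause unless the woman is permanently sterile. It then lists the categories of women who are not WOCBP. The second category is the postmenopausal woman: "A postmenopausal state is defined as age 60 years or older or no menses for 12 months without an alternative medical cause". Under that category is the HRT bullet. It opens: "Female on HRT and whose menopausal status is in doubt will be required to use one of the nonestrogen hormonal highly effective contraception methods", on condition that she wishes to stay on HRT during the study. The next sentence reads: "Otherwise, they must discontinue HRT to allow confirmation of postmenopausal status before study enrollment".

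Two other sections bear on this. Section 5.3.4 says: "Female participants will not require use of contraception as they cannot be women of childbearing potential". Section 10.4.4 introduces the list of methods with: "The following contraception methods are be used by women of childbearing potential who are partners of male participants in this study".

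**The concern.** The HRT bullet offers two routes, and only the second requires postmenopausal status to be confirmed before enrolment. On the first route a woman whose status is openly in doubt takes contraception instead. Contraception manages childbearing potential; it does not show that there is none. An eligibility rule that excludes childbearing potential outright therefore rests on a definition that lets an unresolved case through.

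The restriction has a stated safety basis. A site that reads the HRT bullet literally could enrol a woman that a site reading Section 5.1 literally would turn away. Section 5 does not permit eligibility waivers, so sites need a single rule and at present have two.

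**Working it through.** There is no figure in the plan to reproduce for this point. The check sets the provisions side by side and then bounds the number of women affected.

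**Comparison of the provisions**

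| Protocol section | Rule for a female participant | Fits the first HRT route? |
|---|---|---|
| 4.2.1 | Non-childbearing potential only, for lack of embryofetal toxicity data | No |
| 5.1, criterion 1 | Non-childbearing potential, no exception | No |
| 5.3.4 | No contraception needed, since none can be a WOCBP | No: the bullet requires contraception |
| 10.4.2 | WOCBP not eligible | No, unless doubtful status counts as non-WOCBP |
| 10.4.3, opening | Fertile until postmenopausal unless permanently sterile | No: doubtful status does not rebut this |
| 10.4.4 | Methods addressed to partners of male participants | Only loosely: the list is not addressed to her |

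**Reasoning**

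1. Section 10.4.3 starts from fertility. A woman leaves that default by being permanently sterile or postmenopausal.
2. If her menopausal status is in doubt, neither has been established.
3. The first route lets her continue HRT during the study, which has meaning only if she is a participant.
4. Pre-enrolment confirmation appears only in the sentence beginning with the word otherwise, so the first route does not require it.
5. Section 10.4.3 describes FSH confirmation for women who use neither hormonal contraception nor HRT. A woman on the first route uses HRT, so that confirmation does not apply to her.
6. The first route is thus inconsistent with Sections 4.2.1, 5.1, 5.3.4 and 10.4.2.

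**Size**

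Inputs are the cohort numbers in Section 4.1, without replacements.

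- Planned maximum: Part A 5 × 10 = 50, Part B 2 × 15 = 30, Part C 2 × 10 = 20; total 50 + 30 + 20 = 100.
- On active drug: 5 × 8 + 2 × 12 + 2 × 8 = 40 + 24 + 16 = 80.
- Age 60 or older is postmenopausal by definition, and permanently sterile women fall under a separate category. The clause therefore reaches only women under 60, on HRT, not permanently sterile, with unresolved status.
- The documents give no share for this group. Assuming 0% to 3% of participants: 0 × 100 = 0 to 0.03 × 100 = 3 women.

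**Safeguards already in the protocol**

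The bullet itself requires contraception. Participants are confined to the research unit during dosing (Section 4.2.2). The investigator reviews medical, menstrual and recent sexual history (Section 10.4.2). Contraception review is on the Schedule of Activities (Tables 1, 3 and 5), although Section 5.3.4 describes that conversation for male participants only. Confinement does not deal with a pregnancy that began before admission, and it ends about three days after the last dose. The bullet gives no duration for contraception after dosing, whereas Section 10.4.1 sets at least 28 days for men. Nothing here rests on pregnancy testing, because parts of the schedule are redacted.

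**The case against.** The strongest reply concerns where the bullet sits. It falls under the postmenopausal category, beneath a clinical definition based on age or 12 months without menses. The preceding bullet makes FSH confirmation optional and offers it only to women off HRT. On this view the HRT bullet is about a woman already placed in the category whose status FSH cannot confirm while she takes HRT, and contraception is an added precaution. The conflict would then shrink to a loose sentence in Section 5.3.4. This reading does not fit the text: a woman who clearly met the 12-month definition would not be described as having doubtful menopausal status.

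A second reply is that criterion 1 and Section 10.4.2 control, and the bullet never says she is eligible. But both provisions take their meaning from Section 10.4.3, so they cannot simply override it. If they did, the first route would have no use and should be deleted anyway.

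A third reply is that making HRT discontinuation the only route raises timing questions. FSH is listed as a screening-only test in Table 14, no washout is stated, and the visible text of Section 5.4 bars rescreening of screen failures. The gap is real, but it already exists, because stopping HRT is the protocol's own second route.

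Three parts of the other side stand. The point about Section 10.4.4 is minor, since a site can pick nonestrogen hormonal methods from that list. The 0% to 3% range is an assumption that includes nobody. The practical risk is limited by the safeguards listed above.

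**Conclusion.** The concern holds. Section 10.4.3 allows participation on HRT plus contraception without confirmed postmenopausal status, while the rest of the protocol admits only women of non-childbearing potential and says they need no contraception. The rule contradicts itself on a matter the protocol justifies by safety, and it is wrong as written.

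It is a minor point: few women could be affected, and no endpoint, sample size or analysis changes. The conclusion about the text does not depend on the assumed proportion. It depends on reading doubtful status to mean that the postmenopausal definition has not been shown to be met, which is the natural reading of the words.

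**What to change.** Delete the contraception option from the HRT bullet in Section 10.4.3 and keep only confirmation. Suggested wording: *A woman on HRT whose menopausal status is in doubt must stop HRT and have postmenopausal status confirmed before she is enrolled; if this is not done, she is not eligible.* Sections 4.2.1, 5.1, 5.3.4 and 10.4.2 then agree with it unchanged.

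The cost is an edit to one bullet, with no change to the Schedule of Activities. A few women who will not stop HRT become ineligible, as criterion 1 already implies. The sponsor could use the same edit to say how long HRT must be stopped before the screening FSH sample, which the visible text leaves open.

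If the sponsor meant the bullet only for women who already meet the 12-month definition, it should say so, drop the reference to doubtful status, and add the resulting contraception exception to Section 5.3.4. That is a larger edit.
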